3.2 Secondary Objectives

The secondary objectives of the study are

1. To determine the progression free survival measured from time of enrollment to first evidence of progressive disease and evaluated 3 months after treatment initiation.
2. To determine the local control measured from time of enrollment to first evidence of progressive disease at the treatment site and evaluated 3 months after treatment initiation
3. To determine the incidence of grade ≥ 3 , pneumonitis 6 months of completing SBRT
4. To determine the influence of number of metastatic sites on OS, and PFS.

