2.0 PROPOSED TRIAL RATIONALE

Anti-PD-1 antibodies have demonstrated activity in the treatment of lung cancer. Opdivo was approved in February of 2015 by the FDA for patients with metastatic squamous NSCLC with progression on or after platinum based therapy. In the open-label trial, patients were randomized to receive OPDIVO (n=135) administered at 3mg/kg every 2 weeks. Median survival was improved to 9.2 months compared to 6 months in patients receiving docetaxel (n=137) 75mg/m² every 3 weeks, p=0.00025. Median progression free survival was slightly improved to 3.5 months compared to 2.8 months but 1 year overall survival was improved to 42% compared to 24% (36).

We expect that improvements in local control, increased immunogenic response and abscopal effect seen with combined modality treatment will result in improved local control, progression free survival and resultant significant increases in overall survival beyond 3 months. We propose a pilot/phase II study to assess the safety and efficacy of combination immunotherapy and stereotactic ablative radiation therapy (I-SABR).

Treatment will be a sequential combination treatment of SABR/SBRT and immunotherapy to assess the safety and feasibility of treatment. SABR/SBRT will be administered in 3-5 daily treatments followed by immunotherapy following the conclusion of SABR/SBRT. This approach will take advantage of the transient increase in antigen availability, increased antigen presentation and upregulation of PD-1 by tumor cells following ablative radiation therapy. After an interim safety analysis, the study will continue to the phase II portion where overall survival, progression free survival and response rate will be the primary and secondary end points. For reference, outcomes will be compared to the immunotherapy arms of checkmate 057 and Keynote 042 trials.

Several trials examining combination I-SABR are currently underway. A table of selected studies is included in [Table 1](#).

Study (Institution)	SABR Target	Dose (Gy/Fractionation)	Immunotherapy Agent	Sequence
NCT02239900 (MD Anderson Cancer Center)	Liver Lung Adrenal	50/4 60/10	Ipilimumab	Concurrent/Sequential
NCT01862900 (Chiles Research Institute)	Lung Liver	15/1 201/1	Anti-OX40	Concurrent
NCT01769222 (Stanford University)	Any	20/2	Ipilimumab	Concurrent
NCT02298946 (NIH/NCI)	Liver	8/1 24/3	PD-1 Inhibitor	Sequential

Table 1. List of selected ongoing I-SABR studies

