2.1 RATIONALE FOR DOSE SELECTION

A. Radiation Therapy: All patients in this trial will be treated with fractionated Stereotactic body radiation therapy. Treatment of oligometastatic lung cancer in this fashion has been explored in multiple studies with encouraging long term survival data (37-39). In a recent multi-institutional randomized trial from MD Anderson cancer center, patients with oligometastatic lung cancer where randomized to systemic therapy plus SBRT to all metastatic sites versus systemic therapy alone (40). The study was terminated early after a planned interim safety analysis showed significantly improved in progression free survival in the SBRT group (11.9 vs 3.9 months) at median follow up of 12 months. Patients in the SBRT group were less likely to develop new lesions compared to patients on systemic therapy alone suggesting SBRT acted similarly to systemic therapy.

In a series of mouse tumor models treated with an anti-CTLA-4 antibody combined with 3 different radiation regimens, enhanced tumor responses were observed when treated with fractionated radiation regimens of $8 \text{ Gy} \times 3$ or $6 \text{ Gy} \times 5$ administered on consecutive days, but not with $20 \text{ Gy} \times 1$ (19). The fractionated regimens, but not the single radiation dose, also resulted in abscopal effects. For uniformity, we will adhere to the radiation dose guidelines as prescribed in the NRG-BR001 protocol examining the role of SBRT for oligo-metastatic disease (41). Dose reductions are allowed to pre-specified doses at the treating physician's discretion if dosimetric criteria are not achievable. Dose schedules and prescriptions are described under radiation treatment.

B. Immunotherapy: All patients in this trial will be treated with either Nivolumab or Pembrolizumab at FDA approved dosing and indications (1, 36). If new FDA approved anti-PD-1 therapies emerge during the study duration, the study will be modified with IRB approval to allow addition of newly approved therapies to the protocol. (36). These FDA approved dosing schedules are established and have a favorable toxicity profile and will allow direct comparison of outcomes to immunotherapy alone trials vs immunotherapy plus SBRT.

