4.1 STUDY DESIGN AND DURATION

This is a combination single arm pilot/Phase II study of combination I-SABR for metastatic NSCLC. Treatment safety and feasibility will be assessed in the initial pilot phase and oncologic outcomes will be assessed in the second phase.

After screening, patients will receive 3-5 fractions of SBRT/SABR to up to 3 metastatic sites in addition to the primary tumor. Following the conclusion of SBRT/SABR, patients will receive Immunotherapy therapy at standard dosing until disease progression or discontinuation of treatment due to toxicity or patient choice (Figure 1).

Tumor assessment will be performed prior to SABR initiation and every 3 months or for clinical disease progression.

Figure 1: Sample Patient Treatment and Follow-Up Timeline

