4.4 Duration of Study

The study will conclude 24 months after the last patient is accrued. Given the poor prognosis and short overall survival in patients with metastatic NSCLC, all end-points should be realized within 24 months. At the conclusion of the study, patients and investigators may decide to continue with Immunotherapy treatment. We expect to enroll 100 patients over 2 years.

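### PFS is defined without death as an event, so it is time to progression under a PFS label and can only read equal to or above true PFS; the written progression rules also omit new lesions

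*Protocol*

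**What the plan says.** Protocol Section 3.2, item 1, fixes the start, the event and the evaluation time: "To determine the progression free survival measured from time of enrollment to first evidence of progressive disease and evaluated 3 months after treatment initiation". Item 2 defines local control on the same pattern, restricted to the treated site. Item 4 reuses the endpoint: "To determine the influence of number of metastatic sites on OS, and PFS". Section 5.3 plans a PFS analysis of the whole cohort at study end.

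On assessment, Section 4.1 states: "Tumor assessment will be performed prior to SABR initiation and every 3 months or for clinical disease progression". The written rules for progressive disease are in Section 6.7 (growth in the sum of target-lesion diameters) and Section 6.8 (clear worsening of non-target lesions already present). Neither mentions new lesions. RECIST 1.1 is named only in the measurable-lesion eligibility criterion (Section 5.1, repeated in Addendum 2), where it is linked to response assessment.

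On use of the results, Section 2.0 lists PFS among the phase II end points and continues: "For reference, outcomes will be compared to the immunotherapy arms of checkmate 057 and Keynote 042 trials". Section 2.1 says that the approved dosing schedules "will allow direct comparison of outcomes to immunotherapy alone trials vs immunotherapy plus SBRT". The hypothesis statement with version 6.0 expects longer PFS than with PD-1 monotherapy.

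**The concern.** PFS ordinarily ends at progression or death, whichever comes first. The definition here ends at progression only, and nothing else in the protocol brings death back in. An analyst who follows it must censor a patient who dies without documented progression, or treat the death as a competing event. Either way the patient does not count as a PFS failure.

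The 3-month evaluation makes early deaths matter more. The first scheduled follow-up scan falls at about that time, so a patient who dies earlier, without a scan prompted by clinical progression, has no event at the very time point of interest. The protocol expects substantial mortality: "Given the poor prognosis and short overall survival in patients with metastatic NSCLC, all end-points should be realized within 24 months".

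With no concurrent control arm, nothing shares the distortion. It pushes PFS in the direction of the hypothesis without any treatment effect, and objective 4 and the final PFS analysis inherit it.

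The second, smaller point is the missing new-lesion clause. Read literally, Sections 6.7 and 6.8 do not make a new metastasis on its own progressive disease. That would also move progression later.

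**Working it through.** The protocol gives no PFS sample size, event count or power, so there is no figure of its own to reproduce.

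**Step 1: direction.** Suppose deaths before progression are censored. At each event time *j* the number at risk *n_j* is the same as for true PFS. The counted events *x_j* (progressions) are a subset of the true events *e_j* (progressions plus deaths). Hence 1 − *x_j*/*n_j* ≥ 1 − *e_j*/*n_j* for every Kaplan-Meier factor, and the curve as defined is never below true PFS. In 2,000 simulated trials of 100 patients with random censoring there was no exception. The two curves coincide only if nobody dies before documented progression.

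**Step 2: illustrative size.** Inputs:
- Median PFS 3.5 months, from the nivolumab versus docetaxel trial in Section 2.0: "Median progression free survival was slightly improved to 3.5 months compared to 2.8 months". The protocol does not identify this trial as either of the two named reference trials.
- Share *d* of first events that are deaths: not in the documents; assumed 10%, 20%, 30%.
- Exponential, independent event types, and a common time origin for enrollment and treatment start (assumptions).

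Formulas:
- λ = ln 2 / 3.5 = 0.198 per month
- True S(3) = exp(−3 × 0.198) = 0.552
- As defined, deaths censored: S(3) = 0.552^(1−d); median = 3.5/(1−d)
- As defined, death as competing risk: progression-free proportion = 1 − (1−d)(1 − 0.552)
- Uncounted deaths by 3 months per 100 patients = 100 × d × (1 − 0.552)

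| d (assumed) | 3-month figure, deaths censored | Shift (points) | Median (months) | 3-month figure, competing risk | Uncounted deaths per 100 |
|---|---|---|---|---|---|
| 0 | 55.2% | 0 | 3.50 | 55.2% | 0 |
| 10% | 58.6% | 3.4 | 3.89 | 59.7% | 4.5 |
| 20% | 62.2% | 7.0 | 4.38 | 64.2% | 9.0 |
| 30% | 66.0% | 10.8 | 5.00 | 68.6% | 13.4 |

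**Step 3: a ceiling on d.** Section 2.0 reports for the same trial: "Median survival was improved to 9.2 months compared to 6 months in patients receiving docetaxel". The overall death hazard is ln 2 / 9.2 = 0.0753 per month. If patients without progression die no faster than the average patient, d cannot exceed 0.0753/0.198 = 0.38 (equivalently 3.5/9.2). At that ceiling S(3) = 0.552^0.62 = 69.2%, the median is 5.65 months, and 17.0 deaths per 100 go uncounted. As a check on the exponential form, 0.5^(12/9.2) = 40.5%, against the 42% one-year survival in Section 2.0.

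**Step 4: sensitivity to the median.** With the 11.9-month median PFS of the SBRT group in Section 2.1, true S(3) = 0.5^(3/11.9) = 84%. Shares of 10%, 20% and 30% give 85%, 87% and 88%, a shift of about 1 to 5 points.

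No figure is offered for the new-lesion point.

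**The case against.** The strongest reply is that Section 3.2 is a one-line objective, that the endpoint is named PFS, and that event and censoring conventions usually belong in an SAP, which may exist. That would answer a silent protocol. This one states the terminating event. An SAP that follows it inherits the error, and one that counts deaths contradicts the protocol.

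Several narrower objections stand in part:
- Section 4.4 speaks of all deaths, whereas the bias needs deaths before documented progression. Scans for clinical progression and the 30-day visit in Appendix III (Table 6.0) will reduce undocumented progressions. They limit the size of the bias but do not change its direction.
- The subject of the comparison sentence in Section 2.1 is the drug dosing schedules, so it is weak evidence of a planned PFS comparison. Section 2.0 and the hypothesis statement carry that point, and Section 2.0 does so only for reference, with no test or threshold.
- The death shares are assumed, and the 38% ceiling needs constant hazards and a trial in previously treated squamous disease. The figures are illustration only.
- Sections 6.7 and 6.8 classify lesions by type and do not claim to be the complete rule for patient-level progression. An assessor may apply RECIST 1.1 and count new lesions anyway. That point is therefore a request for clarification.

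**Conclusion.** The PFS definition is wrong as written for its label. Following it yields time to progression, which reads equal to or above true PFS at every time point; this needs no assumption about hazards. The amount is unknown. Under the stated assumptions it is about 3 to 11 percentage points at 3 months and 0.4 to 1.5 months in the median for death shares of 10% to 30% at a 3.5-month median, and less if progression is slower. The documents do not give the reference trials' PFS definitions, so the claim is against true PFS and not against any particular published figure.

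It should be fixed because PFS is part of the hypothesis in a trial without a control arm. It does not touch overall survival, the phase II primary objective, and no sample size or decision rule depends on it. The new-lesion gap is secondary and acts in the same direction where assessors follow the written rules literally.

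**What to change.** In Section 3.2, item 1, define PFS as the time from enrollment to the earlier of documented progression or death from any cause. If progression alone is really intended, rename the endpoint time to progression and do not set it beside PFS from other trials. Item 4 and Section 5.3 then follow whichever definition is chosen.

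In Sections 6.7 and 6.8, add the appearance of new lesions as progressive disease, or state that progression for PFS is determined by RECIST 1.1.

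The cost is a wording amendment. Deaths are already needed for overall survival, so no new data are required. Reported PFS will be less favourable, or at best unchanged, and because the study is already at version 6.0, earlier scans may need their progression status rechecked for new lesions.

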4. STUDY DESIGN

[figure not shown]
4.1 STUDY DESIGN AND DURATION

This is a combination single arm pilot/Phase II study of combination I-SABR for metastatic NSCLC. Treatment safety and feasibility will be assessed in the initial pilot phase and oncologic outcomes will be assessed in the second phase.

After screening, patients will receive 3-5 fractions of SBRT/SABR to up to 3 metastatic sites in addition to the primary tumor. Following the conclusion of SBRT/SABR, patients will receive Immunotherapy therapy at standard dosing until disease progression or discontinuation of treatment due to toxicity or patient choice (Figure 1).

Tumor assessment will be performed prior to SABR initiation and every 3 months or for clinical disease progression.

Figure 1: Sample Patient Treatment and Follow-Up Timeline

4.2 Radiation Therapy

Radiation therapy will be delivered using SABR or SBRT using the CyberKnife radiosurgery system. Treatment will be delivered in 3-5 fractions as specified in **Table 2**. SBRT can be directed to up to three separate metastatic sites in addition to the primary tumor. Symptomatic or at risk disease sites should be prioritized. Strict adherence to dosimetric criteria is required. If dosimetric criteria cannot be met with stipulated doses, a default dose of 30-40 Gy in 5 fractions will be prescribed. In all cases, a minimum dose of 95% of the prescribed dose is must be delivered to the PTV to satisfy protocol constraints. 90% will be considered an acceptable minimal deviation.

4.3 Immunotherapy

Immunotherapy will be delivered in the form of PD-1/PD-L1 blockade using approved anti PD-1/PD-L1 agents. Dose reductions are appropriate for toxicity as specified or at the discretion of the treating medical oncologist. Prior immunotherapy as part of multi-drug therapy or monotherapy is acceptable prior to initiation of SBRT.

The DLT observation period for continuation or discontinuation of therapy is defined as 14 days starting with cycle 1, day 1. To be evaluable for DLT, a patient must have received at least the first 2 administrations and be monitored for at least 14 days following the first administration. Any of the below outlined events occurring during each DLT observation period and considered to be at least possibly related to Nivolumab will qualify as a DLT.

Non-Hematologic Toxicity

1. Grade ≥ 2 uveitis
2. Any Grade ≥ 3 non-hematologic toxicity except
 - a. Nausea, vomiting or diarrhea
 - b. Clinically insignificant laboratory abnormalities
 - c. Grade 3 infusion reactions that respond to medical management
 - d. Grade 3 immune related effects other than uveitis that improve within 7-14 days with steroid treatment (Appendix 1).

Hematologic Toxicity

1. Grade 4 neutropenia lasting more than 1 week
2. Grade 4 thrombocytopenia
3. Grade 3 thrombocytopenia with bleeding
4. Grade ≥ 3 febrile neutropenia

Special

1. Grade ≥ 2 pneumonitis

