3. STUDY OBJECTIVES

3.1 Primary Objectives

The primary objective of the pilot phase of the study is to characterize the safety, feasibility and tolerability of sequential combination I-SABR in patients with metastatic NSCLC. The first 20 patients will be evaluated for 15 weeks following treatments with I-SABR prior to continuing enrollment. In the Brahmer trial, 5% of patients in the Nivolumab arm developed pneumonitis with a median time to onset of treatment related pulmonary events of 15 weeks. All but one patient with pulmonary events were treated with glucocorticoids and all cases resolved with a median time to resolution of 5 weeks (range 0.6-12.1 weeks).

If more than 5% of patients develop grade ≥ 3 pneumonitis during the initial evaluation phase, no lung directed therapy will be permitted during the phase II portion.

The primary objective of the phase II portion of the study will be overall survival.

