7. IMMUNOTHERAPY

Immunotherapy administration will commence or continue following the conclusion of SBRT/SABR.

Immunotherapy will be administered as an IV infusion as specified. It is not to be administered as an IV push or bolus injection. At the end of the infusion the administration line will be flushed with a sufficient quantity of normal saline per standard of care. Infusions will continue on a standard schedule for the specific immunotherapy agent with pre-treatment assessments for adverse effects using a standard questionnaire.

Immunotherapy administration will be delayed in the case of any of the following:

Any Grade ≥ 2 non-skin, drug-related adverse event, with the following exceptions:— Grade 2 drug-related fatigue or laboratory abnormalities do not require a treatment delay

Any Grade 3 skin, drug-related adverse event

Any Grade 3 drug-related laboratory abnormality, with the following exceptions for lymphopenia, leukopenia, AST, ALT, or total bilirubin:

- Grade 3 lymphopenia or leukopenia does not require dose delay
- If a subject has a baseline AST, ALT or total bilirubin that is within normal limits, delay dosing for drug-related Grade ≥ 2 toxicity
- If a subject has baseline AST, ALT, or total bilirubin within the Grade 1 toxicity range, delay dosing for drug-related Grade ≥ 3 toxicity

Any adverse event, laboratory abnormality, or intercurrent illness which, in the judgment of the investigator, warrants delaying immunotherapy administration.

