With these changes in the immunotherapy landscape, it is highly likely that patients with lung cancer will be increasingly exposed to immunotherapy agents earlier in the treatment course making them ineligible for our study since we currently exclude patients with prior immunotherapy treatments.

Early data with sequential or combination SBRT suggest increased immunotherapy efficacy with similar rates or minimal changes in the toxicity profile of immunotherapy agents (4-5). Since our initial eligibility criteria was designed to limit excess patient toxicity and current available data suggests a combination/sequential regimen is safe, it is prudent that we revise our inclusion/exclusion criteria.

We hereby propose that patients with prior/ongoing immunotherapy treatment be eligible for participation in this study. The eligibility criterion has been modified as such to reflect this change.

References

1. Ghandi L. et al. Pembrolizumab plus Chemotherapy in Metastatic Non-Small-Cell Lung Cancer. *N Engl J Med* 2018; 378:2078-2092
2. Lopes G. et al. Pembrolizumab (pembro) versus platinum-based chemotherapy (chemo) as first-line therapy for advanced/metastatic NSCLC with a PD-L1 tumor proportion score (TPS) $\geq 1\%$: Open-label, phase 3 KEYNOTE-042 study. *J Clin Oncol* 36, 2018 (suppl; abstr LBA4).
3. AstraZeneca Press Release 05/2018: <https://www.astrazeneca.com/media-centre/press-releases/2018/imfinzi-significantly-improves-overall-survival-in-the-phase-iii-pacific-trial-for-unresectable-stage-iii-non-small-cell-lung-cancer-25052018.html>

4. Theelen W. et al. Randomized phase II study of pembrolizumab after stereotactic body radiotherapy (SBRT) versus pembrolizumab alone in patients with advanced non-small cell lung cancer: The PEMBRO-RT study. *J Clin Oncol* 36, 2018 (suppl; abstr 9023)
5. McArthur H. et al. A phase II, single arm study assessing the efficacy of pembrolizumab (Pembro) plus radiotherapy (RT) in metastatic triple negative breast cancer (mTNBC). *J Clin Oncol* 36, 2018 (suppl; abstr 9023)

CLINICAL STUDY PROTOCOL

Protocol Title: A PROSPECTIVE TRIAL OF IMMUNOTHERAPY AND STEREOTACTIC BODY RADIOTHERAPY (SBRT) FOR THE TREATMENT OF METASTATIC LUNG CANCER: SBRT SENSITIZATION OF THE PROGRAMMED DEATH-1 (PD-1) EFFECT

VERSION 6.0, 06/18/2018

Clinical Phase: Pilot/Phase II

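### The 14-day DLT period has no defined start for patients continuing immunotherapy after SBRT, and it is too short for the pneumonitis event on its own list

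*Protocol*

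**What the plan says.** **Window.** Protocol Section 4.3: "The DLT observation period for continuation or discontinuation of therapy is defined as 14 days starting with cycle 1, day 1". The same paragraph later speaks of each such period, although it defines only one.

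**Evaluability.** To count for DLT, "a patient must have received at least the first 2 administrations and be monitored for at least 14 days following the first administration".

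**Attribution.** Listed events "considered to be at least possibly related to Nivolumab will qualify as a DLT". The list includes Grade ≥ 2 pneumonitis as a special item, alongside uveitis, other non-hematologic toxicity and hematologic toxicity.

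**Who enters.** Section 4.3: "Prior immunotherapy as part of multi-drug therapy or monotherapy is acceptable prior to initiation of SBRT". Study Addendum 2 proposes that "patients with prior/ongoing immunotherapy treatment be eligible for participation in this study". Section 7: "Immunotherapy administration will commence or continue following the conclusion of SBRT/SABR".

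**Timing of pulmonary toxicity.** Section 3.1 cites, for the nivolumab arm of an earlier trial, pneumonitis in 5% of patients and "a median time to onset of treatment related pulmonary events of 15 weeks". The same section evaluates the first 20 patients for 15 weeks after treatment. Its only numeric rule there concerns Grade ≥ 3 pneumonitis.

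**The concern.** The DLT period reads as if every patient starts immunotherapy after SBRT. Addendum 2 changed who can enter but left the period as it was. For a patient already on treatment, the protocol does not fix which cycle starts the clock. Two assessors could therefore classify the same post-SBRT event differently, one as a DLT and the other as falling outside the window.

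For patients starting afresh the start is clear, but the window is short against the protocol's own figure for pulmonary onset. Pneumonitis is the toxicity that Section 3.1 singles out.

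The pilot's primary objective is safety, feasibility and tolerability of the sequence. The Section 4.3 list is the protocol's only definition of dose-limiting events, and the only place where Grade 2 pneumonitis counts. If pilot DLTs are reported under the stated window, a low count could be taken as good tolerability when it partly reflects the clock.

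**Working it through.** The protocol derives no figure on this point, so there is none to reproduce. Four checks follow.

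**1. Start of the window, by type of patient**

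| Patient | Cycle 1 = first ever given | Cycle 1 = first after SBRT |
|---|---|---|
| Starts immunotherapy after SBRT | Window follows SBRT | Window follows SBRT |
| On ongoing immunotherapy, past its first 14 days | Window closed before SBRT; no later event qualifies | Window follows SBRT |

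The text does not choose between the columns. Only the second row is affected.

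**2. Length of the window against pulmonary onset**

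Inputs: window of 14 days = 2 weeks (Section 4.3); median onset of 15 weeks = 105 days (Section 3.1). The ratio is 14/105 = 13.3%.

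Only the median is given, so the shape of the onset distribution is an assumption. With a Weibull shape k, the share of events that have started by week t is F(t) = 1 − 2^(−(t/15)^k).

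| k | Share by week 2 | Share by week 15 |
|---|---|---|
| 0.75 | 14.2% | 50% |
| 1 (exponential) | 8.8% | 50% |
| 1.5 | 3.3% | 50% |
| 2 | 1.2% | 50% |

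The window would miss about 86% to 99% of such events. The calculation assumes that the cited onset is measured from the start of immunotherapy and carries over to treatment after SBRT. The documents establish neither.

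**3. What this means in 20 patients**

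As an illustration, take the cited 5% as the pneumonitis rate. Expected cases are 20 × 0.05 = 1.0.

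- By day 14: 1.0 × 0.088 = 0.09 cases (0.01 to 0.14). The chance of at least one is 1 − (1 − 0.05 × 0.0883)^20 = 8% (1% to 13%).
- By week 15: 1.0 × 0.50 = 0.50 cases. The chance of at least one is 1 − (1 − 0.025)^20 = 40%.

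The 5% is not broken down by grade and comes from nivolumab without SBRT, so these figures show scale only.

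**4. Evaluability against the window**

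The window covers days 1 to 14. On the 2-week interval cited in Section 2.0 for nivolumab, the second dose falls on day 1 + 14 = 15. On the 3-week interval cited in Study Addendum 1 for pembrolizumab, it falls on day 1 + 21 = 22. Both are after the window. Evaluability is thus settled after the period closes, by a dose that the event itself may prevent: Appendix I discontinues immunotherapy for Grade 3–4 pneumonitis. Read literally, a patient with such an event before the second dose is not evaluable for DLT.

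**The case against.** The strongest reply is that Section 4.3 words the period as a rule for continuing or stopping therapy in the individual patient. No DLT rate, DLT stopping boundary or study decision is planned. Pilot safety runs on a separate track: the 15-week evaluation in Section 3.1 with its Grade ≥ 3 pneumonitis rule, the 6-month pneumonitis objective in Section 3.2, and the adverse event assessments after SBRT in Appendix III. This stands, and it limits the weight of the point. It does not supply a definition of the other Section 4.3 events after SBRT, and the numeric rule leaves out Grade 2 pneumonitis.

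Two stronger readings are tempting, and the documents support neither.

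- A reader might infer that the clock predates SBRT in every patient already on immunotherapy, so that their DLT count is zero by construction. That is one reading of an undefined term. Section 4.1 places immunotherapy after SBRT, so cycle 1 can also mean the first on-study cycle. A patient who stopped earlier immunotherapy and restarts after SBRT may reasonably be given a new cycle 1.
- A reader might infer that DLT data cannot describe tolerability of the combination at all. The 15-week figure covers pulmonary events under nivolumab only. It says nothing about when the hematologic, ocular or other listed events occur.

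It is also unknown how many of the first 20 patients were on ongoing immunotherapy. Addendum 2 says prior immunotherapy was excluded until then, and the protocol does not say how many had enrolled by that time.

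**Conclusion.** The point holds in a limited form. The start of the DLT period is undefined for patients with ongoing immunotherapy. Under either reading, the 14 days would capture only about 9% of pulmonary events (1% to 14%), given the protocol's own 15-week median and an assumed Weibull shape between 2 and 0.75. The two-dose condition falls outside the window on both cited schedules. Attribution to nivolumab alone does not match the agents allowed in Sections 2.1 and 4.3 and Addendum 1.

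The size estimate concerns pulmonary events only. Because no study-level decision depends on a DLT count, this is not a defect that must be cured before the trial can proceed. It does warrant a wording amendment, since DLTs reported under the stated window would leave out most events of the kind the pilot was set up to watch.

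**What to change.** For reporting the pilot's tolerability only, tabulate the Section 4.3 events that occur after SBRT. Count them from the first post-SBRT administration through the existing 15-week evaluation, attribute them to any allowed agent, and show patients starting and patients continuing immunotherapy separately.

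The cost is a short amendment. Adverse effects are already assessed before infusions (Section 7) and at follow-up visits (Appendix III). The reported event rate will be higher than under the 14-day window, and by the cited median about half of pulmonary events would still start after 15 weeks; the report should say so.

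The 14-day continuation or discontinuation rule, its starting point and its two-dose condition in Section 4.3 contradict or do not fit Sections 3.1 and 7 and Study Addendum 2. The investigator must reconcile them. No treatment rule is proposed here.
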